### **2.3.4 Study Periods**

All periods below end at the study completion or early withdrawal visit. For all periods, NALT refers to the first occurrence of NALT post study-treatment.

If a patient is ongoing in any period at the time of reporting, then consider last known alive date as the period end date just for the purpose of duration calculations and to ensure events are still mapped to this period.

#### **2.3.4.1 Treatment Period**

The treatment period will be defined as the time between study day 1 and last administration of any component of the study treatment + 28 days or if a NALT starts within 28 days, then treatment period ends one day prior to the start of the NALT.

#### **2.3.4.2 Induction Treatment Period**

*Only relevant for studies with a maintenance or consolidation treatment period:* For patients receiving maintenance or consolidation therapy, the induction treatment period will be defined as the time between study day 1 and 1 second before the first dose of maintenance or consolidation therapy, or if a NALT starts prior to the start of maintenance or consolidation, the induction treatment period ends one day prior to the start of the NALT. For those not receiving maintenance or consolidation therapy, the induction treatment period follows the same rules as given above for the treatment period (see Section 2.3.4.1).

#### **2.3.4.3 Maintenance or Consolidation Period**

*Only relevant for studies with a maintenance or consolidation treatment period:* The maintenance or consolidation period starts on the day of the patient's first dose of any treatment in maintenance or consolidation and ends one day prior to the start of NALT or 28 days after the last dose of any maintenance or consolidation treatment.

Note: Safety outputs produced on the maintenance or consolidation period will only show the maintenance or consolidation treatment arm, and these outputs will only include those patients that enter the maintenance or consolidation period.

#### **2.3.4.4 Post treatment Follow-up Period**

The follow-up period refers to the phase of the study that is post study treatment. Only patients who have an induction treatment completion eCRF page completed (for patients without a dose of maintenance or consolidation treatment) and a maintenance/consolidation treatment completion eCRF page completed (for patients who received maintenance or consolidation treatment) will be included in the follow-up period.

The follow-up period starts the day after the end of the treatment period (see Section 2.3.4.1). The follow-up period ends at the date recorded on the post treatment follow-up phase completion eCRF page, or at the last recorded date in the eCRF for patients ongoing in the period.

#### **2.3.4.5 Survival Follow-up**

Survival follow-up starts the day after the follow-up period ends. Survival follow-up ends at the date recorded on the study completion/early discontinuation eCRF page, or at the last recorded date in the eCRF for patients ongoing in the period. For patients who withdrew from induction, post-induction or follow up phase due to PD, survival follow up starts the day after the date of study completion/early discontinuation.

### **2.3.5 Treatment Cycle**

A treatment cycle starts on the day of the first administration of a study treatment component and ends the second before the start of the next cycle. For example, cycle 1 will start at the first valid cycle 1 study drug administration and will end at the start date of the cycle 2 dose (or cycle 3, or 4 etc. if cycle 2 dose is missing) minus 1 second. The last cycle ends when the treatment period ends.

### **2.3.6 Observation Time**

Observation time is the time between enrolment date and the day of death or the last assessment in the database (=last known alive date, see Section 2.3.7).

### **2.3.7 Last known alive date**

The last known alive date is derived from the latest of dates in the following CRF fields: AE start and end dates (including start and end dates of IRR symptoms), tumor response assessment dates, study drug exposure dates, lab assessment dates, vital signs assessment dates, ECG assessment dates, survival follow-up pages where the status is confirmed as 'ALIVE', death date, enrolment date and date of informed consent.

As per STREAM standard rules only partial dates from tumor response or death data are included. In this case missing day is replaced by 1st of the month if only month and year are given. Dates where month and/or year are missing are not imputed but excluded. For partial death dates STREAM applies the following additional rule: If month/year of last known alive date from all other dates\* is equal to the month/year of partial death date then last known alive date is set to \* + 1 day.

### **2.3.8 Study Drug Exposure Time**

Study drug exposure time is defined as the last study treatment administration end date (where dose is > 0) minus the first study treatment administration date (where dose is >0) plus 1 day. This could be calculated individually by study drug or collectively for all study drugs.

### **2.3.9 General Rules**

In the analysis of laboratory data by cycle, if there are several observations per cycle the last value is used. If there are two valid assessments per day and no time is available, the scheduled valid assessment will be taken. In the analysis of follow-up data by visit, patients will be assigned to visits using the clinical planned event (CPE).

All derivations of duration are initially done based on days and converted to months and years if needed using 30.4375 and 365.25, respectively, as denominator if not otherwise specified. Unless otherwise specified, months will be used in outputs.

Computation of durations: any duration in days is computed as end date minus start date + 1 day.

## 2.4 Handling of Missing and Incomplete Data

Laboratory values with either a '<' or '>' included in the lab result will have the inequality symbol removed and 0.001 will be either subtracted (when '<' is included) or added (when '>' is included) to the numeric value of the result for the purpose of summarizing (the original value will be displayed in listings). For example, laboratory values given as "<7" or ">7" are treated as follows:

Recorded data value	When reported as numerical value	When reported in a listing
<7	6.999	<7
>7	7.001	>7

Each AE is assigned to a time period, i.e. pre-treatment, during treatment (could be further split as induction/maintenance or consolidation) or follow-up (Section 2.3).

In listings AEs with partial dates will be shown by having a missing study day.

For AEs and concomitant treatment (not including NALTs), the following rules will be applied:

- Incomplete onset dates for AEs will be handled as follows:
  - in case the day is missing, it is replaced by the 1st of the month, unless a trial treatment exists within that month (not necessarily first treatment) then set to the date of that treatment
  - in case the day and month are missing, they are replaced by 1st of January, unless the first trial treatment exists within that year then set to the date of that treatment
  - in case imputation leads to the AE occurring before treatment, the onset date will be set to the treatment start date
  - resolution dates are checked to ensure imputed onset dates do not become later than the resolution date
- In case AE most extreme intensity is missing, it will be replaced by the initial intensity
- AEs with missing grades will be included in the summaries for grade 3 to 5 AEs
- AEs with missing relationship to trial medication are included in the summaries of related AEs
- AE with missing seriousness will be included in all summaries of serious adverse events (SAEs)

- For partial concomitant treatment start dates the 1st of the month will be imputed (if only day is missing) or 1st January will be imputed (if day and month are missing).

Partial dates of NALT will be imputed as follows, in order to use the most conservative (i.e. earliest) date without shortening the treatment period:

- If only the year is available then the difference between 1st January of the year and the last administration date of any component of study treatment will be checked: if the difference is >28 days then 1st January will be imputed; otherwise, if the difference is ≤28 days then the date of the last study drug administration\* + 29 days will be imputed.
- If the month and year are both available then the difference between the 1st of the month and last study drug administration will be checked: if the difference is >28 days then the 1st of the month will be imputed; otherwise, if the difference is ≤28 then the date of the last study drug administration\* +29 days will be imputed. However, if this leads to the imputed date having the month following the month in the partial date, then the last day of the partial date month will be imputed.

\*For B-cell and Immunoglobulin outputs, use the last antibody administration date; for other outputs use the last of all study medication dates.

Partial study drug administration dates will not be imputed. A valid study drug administration record is one with a complete begin date and a >0 actual dose for antibody or chemotherapy. Only valid records should be used for all analyses where information of study drug administration is used.

Handling of partial or missing dates for other assessments are discussed within their corresponding sections.

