### 2.2 Treatment Definition

"Chemotherapy" (CT) is defined as at least one dose > 0 of Doxorubicin, Bendamustine, Cyclophosphamide, Vincristine or Prednisone/Prednisolone/Methylprednisolone (=steroids). Steroids are only counted as part of Chemotherapy if they were given as part of CHOP according to the study drug eCRF page (EX domain).

"Study treatment" is defined as at least one dose > 0 of any component of combination therapy (e.g. obinutuzumab, atezolizumab, polatuzumab vedotin, venetoclax, lenalidomide, idasanutlin) or chemotherapy.

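### SAP 2.4 limits a valid dosing record to antibody or chemotherapy, which contradicts the SAP sections that count idasanutlin and venetoclax

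*SAP*

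**What the plan says.** SAP 2.4 (Handling of Missing and Incomplete Data) first says that partial dosing dates are not imputed. It then says: "A valid study drug administration record is one with a complete begin date and a >0 actual dose for antibody or chemotherapy". The next sentence sets the reach of the rule: "Only valid records should be used for all analyses where information of study drug administration is used".

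SAP 2.2 defines both terms that matter here. Chemotherapy "is defined as at least one dose > 0 of Doxorubicin, Bendamustine, Cyclophosphamide, Vincristine" or a steroid, and steroids count only when given as part of CHOP. Study treatment is any component of the combination, with the examples "e.g. obinutuzumab, atezolizumab, polatuzumab vedotin, venetoclax, lenalidomide, idasanutlin) or chemotherapy". Both oral drugs are therefore study treatment, and neither is chemotherapy.

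SAP 2.3.4.1 sets the treatment period as "the time between study day 1 and last administration of any component of the study treatment + 28 days", cut short the day before new anti-lymphoma therapy if that starts within the 28 days. In SAP 2.4, the footnote to the imputation rule for partial dates of new anti-lymphoma therapy uses the antibody date for B-cell and immunoglobulin outputs. It adds: "for other outputs use the last of all study medication dates".

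**The concern.** The validity rule names two drug classes, and the trial's two oral drugs belong to neither. Applied as written, it removes every idasanutlin and venetoclax record from every analysis that uses dosing. Other parts of the same SAP require those records, and nothing says which text prevails.

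Two kinds of output are exposed:

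- **Exposure.** Protocol 6.2 asks for number of doses, cycles, average dose and relative dose intensity for each treatment component. SAP Outputs 25 and 26 deliver these by drug. The oral drugs are the ones whose doses the trial sets out to find.
- **Period assignment.** The last-dose date fixes the end of the treatment period, and follow-up starts the next day (SAP 2.3.4.4). Adverse events are generally summarised by study period (SAP 6.2.1), and Output 53 splits deaths by period. A last-dose date taken from the antibody alone would place some late on-treatment events in follow-up.

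**Working it through.** The plan gives no figure to reproduce. The check compares the text and then does date arithmetic.

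**Step 1. Do the oral drugs pass the rule?** The antibodies in this trial are obinutuzumab and rituximab. The SAP 2.2 chemotherapy list is doxorubicin, bendamustine, cyclophosphamide, vincristine and CHOP steroids. Idasanutlin and venetoclax are in neither group, so no oral record passes.

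**Step 2. What do other parts of the SAP do with them?**

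| SAP place | Treatment of the oral drugs |
|---|---|
| 2.2 | Both named as study treatment, separately from chemotherapy |
| 2.3.4.1 | Period runs to the last dose of any component + 28 days |
| 2.3.8 | Exposure time may be calculated for each drug, dose above zero |
| 2.4 footnote | Last of all study medication dates, except B-cell and immunoglobulin outputs |
| 6.1.1 | Both count towards a received cycle, dose above zero |

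**Step 3. Inputs for the period end.** These come from Protocol Tables 1 and 4.
- Obinutuzumab: Days 1, 8 and 15 of Cycle 1, then Day 1 of Cycles 2–6.
- Rituximab: Day 1 of Cycles 1–6.
- Idasanutlin: Days 1–5.
- Venetoclax: Days 1–5 or Days 1–10.

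The formula from SAP 2.3.4.1 is: period end = day of last counted dose + 28.

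| Last cycle | All components | Antibody only | Shift |
|---|---|---|---|
| Obinutuzumab Cycles 2–6 or any rituximab cycle, venetoclax Days 1–10 | 10 + 28 = Day 38 | 1 + 28 = Day 29 | 9 days |
| Same, venetoclax Days 1–5 | 5 + 28 = Day 33 | 1 + 28 = Day 29 | 4 days |
| Regimen A, stopping after Cycle 1 Day 15 obinutuzumab | 15 + 28 = Day 43 | 15 + 28 = Day 43 | 0 days |

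**Step 4. Full induction.** Cycle 6 Day 1 is study day 5 × 28 + 1 = 141. Counting antibody only, the period ends on day 141 + 28 = 169. Counting all components, it ends on day 145 + 28 = 173 or day 150 + 28 = 178.

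**Step 5. Post-induction.**
- For patients who go on to maintenance or consolidation, SAP 2.3.4.2 ends the induction period at the first post-induction dose. The 4- or 9-day shift does not apply to their induction period.
- FL patients who complete maintenance receive obinutuzumab for 24 months and the oral drugs for 6 (Protocol Tables 2 and 5). Their last dose is the antibody under either rule, so the shift is 0.
- For DLBCL consolidation the oral schedule is still to be determined. As an assumption only, take rituximab on Day 1 of months 1, 3 and 5, and oral drugs from Day 1 to Day 5 or Day 10 of each month up to month 6. The shift is month length + last oral day − 1. With 28-day months this is 28 + 5 − 1 = 32 or 28 + 10 − 1 = 37 days. With months of 30.4375 days (SAP 2.3.9) it is 34.4 or 39.4 days. The range is about 32 to 39 days.

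**The case against.** The strongest reply is that this is one loosely worded sentence in a section on missing data, placed directly after the statement on partial dosing dates. Its natural job is to screen out records with incomplete dates or zero doses. The specific sections in Step 2 all count the oral drugs, and Output 25 has a block for each study drug. The SAP serves several studies, some with chemotherapy, so the wording looks carried over. It is also meant to be read with a List of Planned Outputs that is not available here. A careful programmer would probably count both drugs.

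Much of this stands. A reader might infer that the SAP has chosen to exclude the oral drugs, and that the tables will be empty and the period shortened. The documents do not support that: both effects follow only if 2.4 is allowed to override the more specific sections. A reader might also infer a loss of about a month across post-induction treatment. That is not supported either, because the shift is zero for FL patients who complete maintenance, and the DLBCL figure rests on an assumed oral schedule. Nor would adverse events drop out of the data. SAP 6.2.1 lists all of them and sets no upper time limit on the follow-up tables.

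The reply does not remove the contradiction. The rule is stated to govern all analyses that use dosing data, and SAP 2.3.5 relies on the word valid to start Cycle 1. A softer reading, in which the dose test applies only to antibody and chemotherapy, leaves the validity rule with no above-zero requirement for the oral drugs. That conflicts with 2.2, 2.3.8 and 6.1.1. The sentence needs repair on either reading.

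**Conclusion.** The point holds as an internal contradiction in the SAP that should be corrected before programming. The intent to count both drugs is clear from the other sections, but the rule as written gives the opposite result and no precedence is stated.

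If it were applied literally, no oral-drug record would be valid for exposure and dose intensity. The treatment period would end 4 or 9 days early for patients whose last treatment falls in induction Cycles 2–6 or any rituximab cycle. That size assumes the antibody is given on Day 1 of the last cycle, the oral course of that cycle is completed, and no new anti-lymphoma therapy cuts the period short. Protocol 4.6.2 allows the other drugs to continue after one is stopped for toxicity due to it alone. If the antibody is the drug stopped, the gap would be longer.

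The effect in DLBCL consolidation cannot be fixed until the oral schedule is known. The primary analysis of CR at end of induction does not use the length of the treatment period and is not affected.

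**What to change.** In SAP 2.4, define a valid dosing record as one with a complete begin date and an actual dose above zero for any component of study treatment. For this trial, name obinutuzumab, rituximab, idasanutlin and venetoclax; for the other studies, refer to the components listed in SAP 6.1.1.

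Add rituximab to the examples in SAP 2.2. That list omits it although 6.1.1 includes it, so a bare cross-reference to 2.2 would leave the DLBCL antibody open to the same literal reading.

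Keep the antibody-only last-dose date for the B-cell and immunoglobulin outputs.

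The cost is one reworded sentence and one added drug name. It needs no new data and leaves the sample size and the primary analysis unchanged.

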### **3 Subgroups**

Definitions of potential subgroups are included in this section. Please refer to LOPO to determine which analyses these subgroups are applied to.

#### **3.1 ABC/GCB subtypes for DLBCL patients**

DLBCL cell-of-origin (COO) prognostic subgroups (ABC and GCB), defined using gene expression profiling, have been associated with different clinical outcomes in patients receiving R-CHOP for DLBCL, with GCB subgroups demonstrating a better prognosis than ABC. DLBCL patients will be classified as having the ABC or GCB cell of origin subtypes.

#### **3.2 BCL-2 subgroups for DLBCL patients**

BCL-2 overexpression has been shown to have prognostic value in DLBCL. DLBCL patients will be classified as having high/low BCL-2 expression.

### 3.3 Double hit subgroup (FISH) for DLBCL patients

Approximately 9%–17% of patients with newly diagnosed DLBCL harbor an underlying *MYC* rearrangement, and these patients are at high risk of treatment failure with R-CHOP. A subset of patients with *MYC*-positive DLBCL also harbors an additional *BCL2* rearrangement. These “double-hit” lymphomas are associated with a very poor outcome Subgroup of ‘Double hit’ DLBCL patients vs. rest of DLBCL patients will be set up.

### 3.4 Double positive subgroup (IHC) for DLBCL patients

Overexpression of BCL-2 and Myc in DLBCL has also been observed in the absence of translocation. This “double-positive” DLBCL status is also associated with worse prognosis. Therefore subgroup of double positive (IHC) DLBCL patients will be set up.

Cell of Origin (COO) and BCL-2 for DLBCL patients: COO and BCL-2 based subgroups will be set up for DLBCL patients: ABC-BCL-2 high, ABC-BCL-2 low, GCB-BCL-2 high, GCB-BCL-2 low.

Cell of Origin (COO) and Myc for DLBCL patients: COO and Myc based subgroups will be set up for DLBCL patients: ABC-BCL-2 positive-MYC positive, GCB-BCL-2 positive-MYC positive.

### 3.5 IPI / FLIPI

For FL patients FLIPI based subgroups may be created. For DLBCL patients IPI based subgroups may be created.

Applicable for Study	BO29563 Atezo-G-B	BO29563 Atezo-G/R-CHOP	BO29562	BO29561	GO29833	GO29834	BH29812
ABC/GCB		x		x			x
BCL-2		x		x			x
Double hit		x		x			x
Double positive		x		x			x
COO&Myc		x		x			x
MRD	x	x	x	x			x
IPI/FLIPI	x	x	x	x			x
p53							x
CD8	x	x	x	x			
PDL1	x	x	x	x			
CD58		x					
CD79				x			

## **4 Demographics, Baseline Disease Characteristics and Prognostic Markers**

### **4.1 Demographics**

Demographics are collected at enrollment and generally may include:

- Gender
- Age at BL
- Race
- Ethnicity
- Weight
- Height
- BMI (= body mass index)
- BSA (= body surface area)
- ECOG Performance score at BL

### **4.2 Baseline Disease Characteristics and Prognostic Markers**

Baseline Disease Characteristics and Prognostic Markers are baseline conditions specifically related to the indication under study. These may include:

- Histology/pathologic diagnosis
- Ann Arbor stage
- Time since first histologic or pathologic diagnosis
- Biomarker status from tumor tissue or blood samples at BL
  - COO
  - BCL-2
  - MYC
  - COO and BCL-2
  - BCL-2 and MYC(FISH)
  - BCL-2 and MYC(IHC)
  - COO and BCL-2 and MYC

- P53 (in studies with idasanutlin)
- IPI
- FLIPI
- Follicular Lymphoma Grade
- Any B symptoms at BL
- Individual B-symptoms, i.e. fever, weight loss, night sweats, at BL
- Bulky disease (threshold 70 mm) at BL
- Number of Indicator Lesions at BL
- Number of non-Indicator Lesions at BL
- Spleen Assessment at BL: Palpable yes/no or >13 cm in vertical length vs. ≤13 cm (r/r DLBCL/FL)
- Liver Assessment at BL : Palpable yes/no
- SPD of Indicator Lesions at BL
- Number of prior anti-lymphoma therapies
- Prior radiotherapies
- Prior surgeries or procedures
- Serum LDH at BL(>normal vs. ≤normal)
- Extranodal Involvement at BL yes/no
- If yes, Number of extranodal sites at BL
- Bone Marrow Involvement
- Status (relapsed/refractory or previously untreated) (BO29563)
- PET score at BL
- Presence of FDG avid lesions representing lymphoma at BL yes/no (detected by PET scan)
- Evidence of FDG avid disease in bone marrow at BL yes/no (detected by PET scan)

## 5 Efficacy Analyses

The efficacy analyses will be performed on the efficacy evaluable population, which includes all patients who received at least one dose of any components of the combination during the expansion

phase. Patients who received any study drugs at the RP2D during the dose-escalation/safety run-in phase may be pooled with the efficacy evaluable population depending on protocol.

*For studies which have specific definition of the efficacy population, refer to protocol for the definition. For example, Study BH29812:* The primary and secondary efficacy analyses will include all patients enrolled in the expansion phase.

## **5.1 Analysis of Primary Endpoint**

The primary efficacy endpoint is the proportion of patients achieving a CR at EOI, as determined by the IRC on the basis of PET-CT scans according to modified Lugano 2014 criteria. Point estimates will be presented, along with the corresponding 90% Clopper-Pearson exact CIs. Patients without a post-baseline tumor assessment will be considered non-responders.

## **5.2 Analysis of Secondary Endpoints**

The secondary efficacy analyses will be estimation of the proportion of patients who achieve each of the following endpoints:

- CR at EOI, as determined by the investigator on the basis of PET-CT scans
- CR at EOI, as determined by the IRC and by the investigator on the basis of CT scans alone
- Objective response (defined as a CR or PR) at EOI, as determined by the IRC and by the investigator on the basis of PET-CT scans
- Objective response (defined as a CR or PR) at EOI, as determined by the IRC and by the investigator on the basis of CT scans alone
- Best response of CR or PR during the study, as determined by the investigator on the basis of CT scans alone

*Study BO29563:*

- CR at EOI, as determined by the investigator on the basis of PET-CT scans using modified Lugano 2014 criteria
- CR at EOI, as determined by the IRC and by the investigator on the basis of PET-CT and CT scans using modified Cheson 2007 criteria
- Objective response (defined as a CR or PR) at EOI, as determined by the IRC and by the investigator using modified Lugano 2014 criteria and modified Cheson 2007 criteria
- Best objective response (defined as a CR or PR) during the study (including all tumor assessments), as determined by the investigator using modified Cheson 2007

Point estimates will be presented, along with the corresponding two-sided 90% Clopper-Pearson exact CIs. Patients without a post-baseline tumor assessment will be considered non-CRs and non-responders, respectively.

